2.1.4.2 Deaths

The observation periods for deaths are per the observation periods defined above.

- Death on-study: deaths occurring during the on-study observation period
- Death on-treatment: deaths occurring during the treatment-emergent adverse event period
- Death post-study: deaths occurring after the end of the study and recorded in the clinical database

2.1.4.3 Laboratory safety variables

Clinical laboratory data consists of blood analysis, including hematology, clinical chemistry, and urinalysis. Clinical laboratory values after conversion will be analyzed in standard international units and international units will be used in all listings and tables.

Blood samples for clinical laboratories will be taken at Visits 1, 2, 6, 10, 14, 20, EOT, EOS and early termination unless otherwise specified. The laboratory parameters will be classified as follows:

- Hematology
 - **Red blood cells and platelets and coagulation:** hemoglobin, hematocrit, total red blood cell count, platelet count
 - **White blood cells:** total white blood cell (WBC) count, neutrophils, lymphocytes, monocytes, basophils, eosinophils
- Clinical chemistry
 - **Metabolism:** glucose, total cholesterol, total protein, creatine phosphokinase, albumin
 - **Electrolytes:** sodium, potassium, chloride, bicarbonate
 - **Renal function:** creatinine, estimated creatinine clearance (Cockcroft's formula in [Section 2.5.1](#)), blood urea nitrogen, uric acid
 - **Liver function:** alanine aminotransferase, aspartate aminotransferase, alkaline phosphatase, lactate dehydrogenase, total bilirubin (in case of values above the normal range, differentiation in conjugated and non-conjugated bilirubin)
 - **Pregnancy test:** serum beta-human chorionic gonadotropin (β -hCG) will be performed at Visit 1 in women of childbearing potential
 - **Hepatitis screen:** clinical laboratory testing at Visit 1 will include hepatitis screen covering hepatitis B surface antigen (HBs Ag), hepatitis B surface antibody (HBs Ab), hepatitis B core antibody (HBc Ab), and hepatitis C virus antibody (HCV Ab).
 - **QuantiFERON-TB Gold / Plus** will be tested at Visit 1
 - **Human immunodeficiency virus (HIV) screen:** anti-HIV-1 and HIV-2 antibodies will be tested at Visit 1

- **Anti-nuclear antibody (ANA)** will be tested at Visit 1

Note: Anti-ds DNA antibody will be tested if ANA is positive ($\geq 1:160$ titer).

Urine samples will be collected:

- **Urinalysis** will be performed at Visit 1, 2, 6, 10, 14, 20, EOT and EOS for specific gravity, pH, glucose, ketones, blood, protein, nitrate, leukocyte esterase, urobilinogen, and bilirubin. If any parameter on the dipstick is abnormal, a urine sample should be sent to the central laboratory for quantitative measurement. If positive for protein and/or red blood cells, microscopic analysis will be performed by the central laboratory.
- **Urine dipstick pregnancy test** will be performed at Visits 2 (prior to randomization), 4, 6, 8, 10, 12, 14, 16, 18, 20, 22, 24, 26, EOT and EOS in women of child bearing potential.

Technical formulas are described in [Section 2.5.1](#).

2.1.4.4 Vital signs variables

Systolic and diastolic blood pressure (mmHg), pulse rate (beats per minute), respiratory rate (breaths per minute), and body temperature ($^{\circ}\text{C}$) will be measured at all visits. Body weight (kg) will be measured at Visit 1, EOT and EOS. Height (cm) will be measured at Visit 1 only.

2.1.4.5 Electrocardiogram variables

Recording of a standard 12-lead ECG will be centrally collected and read for Visits 1, 2, 8, 14, 20, EOT and EOS. At the post-randomization visits, ECGs will be performed prior to investigational product administration. A minimum of 3 complexes in an appropriate lead (lead II) will be averaged to determine the PR-interval, QT/QTc-interval, QRS-complex and heart rate for each ECG. All ECG recordings will be centrally read by independent experts.

2.1.4.6 Physical Examination

Physical examinations will be performed at Visits 1, 2, 8, 14, 20, EOT and EOS including an assessment of skin, nasal cavities, eyes, ears, respiratory, cardiovascular, gastrointestinal, neurological, lymphatic, and musculoskeletal systems. All deviations from normal will be recorded in eCRF, including those attributable to the patient's disease.

2.1.5 Pharmacokinetic (PK) variables

Pre-dose concentrations of SAR440340 in serum at Visits 2, 3, 4, 6, 8, 10, 14, 20 and EOT will be analyzed. Follow-up concentrations will be collected at Visit F1 and EOS. In addition PK will be collected if an SAE or AESI (anaphylaxis, hypersensitivities, ISR, or certain laboratory abnormalities) occur in a patient.

2.1.6 Anti-drug antibody (ADA) variables

The ADA variables are ADA status and titer over time. ADA against SAR440340 samples will be performed at Visits 2, 8, 14, EOT and EOS. If an SAE or AESI (anaphylaxis, hypersensitivities, ISR, or certain laboratory abnormalities) occur in a patient, blood samples will be collected for ADA assessment at or near the onset and completion of the occurrence of the event, if possible.

Patients who discontinue early from treatment may be asked to return to the clinic to have additional PK/ADA samples collected for up to 20 weeks after treatment discontinuation.

2.1.7 Pharmacodynamic (PD)/genomics endpoints

PD endpoints include:

- **Whole blood biomarkers:** blood eosinophil and neutrophil count measured at Visits 1, 2, 4, 6, 8, 14, 20, EOT, F1 and EOS.
- **Serum biomarkers:** total interleukin-33 (IL33), soluble IL33 receptor (sST2) and calcitonin assayed at Visits 1, 2, 4, 6, 8, 14, EOT, F1 and EOS; Total IgE measured at Visits 1, 2, 4, 8, 14 and EOT; pulmonary and activation-regulated chemokine (PARC) measured at Visits 1, 2, 4, 8, 14, 20 and EOT.
- **Plasma biomarkers:** Eotaxin-3 measured at Visits 1, 2, 4, 8, 14, 20 and EOT.
- **Fibrinogen** measured at Visits 1, 2, 14 and EOT.
- Optional PD endpoints (for patients who provide a separate consent for each individual test) include:
 - Pre- and post-bronchodilator FeNO (Fractional exhaled nitric oxide) at Visits 2, 4, 6, 8, 14, 20.
 - Induced sputum for RNA expression at Visits 2, 14 and EOT.
 - RNA samples collected at Visits 1, 2, 4, 14 and EOT.
 - Archived blood samples collected at Visits 1, 2, 4, 8, 14, 20 and EOT.

2.2 DISPOSITION OF PATIENTS

This section describes patient disposition for both patient study status and the patient analysis populations.

Screened patients are defined as any patient who signed the informed consent.

Randomized patients are any patient who has signed informed consent and has been allocated to a randomized treatment regardless of whether the treatment kit was used.

For patient study status, the total number of patients in each of the following categories will be presented in the clinical study report using a summary table:

- Screened patients
- Screen failure patients and reasons for screen failure
- Non-randomized but treated patients
- Randomized patients
- Randomized but not treated patients
- Randomized and treated patients
- Patients who did not complete the treatment as per protocol
- Patients who discontinued the treatment by main reason for permanent treatment discontinuation
- Patients who withdraw from the study
- Patients who withdraw from the study by main reason for study discontinuation
- Status at last study contact (Alive, Deceased)

For all categories of patients (except for the screened and non-randomized categories) percentages will be calculated using the number of randomized patients as the denominator. Reasons for treatment discontinuation will be supplied in tables giving numbers and percentages by treatment group.

Additionally, the analysis populations for safety, efficacy, PK and ADA will be summarized in a table by number of patients on the randomized population.

2.2.1 Protocol deviations

The number and percentage of patients with a critical or major protocol deviation will be summarized by deviation and overall within treatment group. Specific deviations related to randomization may be summarized separately. A listing of patients with at least one critical or major deviation will be provided.

2.3 ANALYSIS POPULATIONS

The randomized population includes any patient who has signed informed consent and has been allocated to a randomized treatment regardless of whether the treatment kit was used or not.

For any patient randomized more than once, only the data associated with the first randomization will be used in any analysis population. The safety experience associated with any later randomization will be assessed separately.

2.3.1 Efficacy populations

The primary efficacy analysis population will be the modified intent-to-treat (mITT) population which includes all randomized patients who have received at least one dose of IMP. Randomized patients will be analyzed according to the treatment group allocated by randomization.

Randomized patients for whom it is unclear whether they took the study medication will be included in the mITT population according to treatment allocated by randomization.

A second efficacy analysis population will be the high eosinophil population which includes all patients in the mITT population with baseline eosinophil count ≥ 250 /mm³.

2.3.2 Safety population

The safety population includes all patients exposed to IMP, regardless of the amount of exposure. Patients will be analyzed according to the treatment actually received. Randomized patients for whom it is unclear whether they took the IMP will be included in the safety population in the group to which they are randomized. Randomized patients who took at least one SAR440340 dose will be included in the SAR440340 group.

2.3.3 Pharmacokinetic analysis population

The PK population will consist of all patients in the safety population with at least one post-dose, non-missing SAR440340 serum concentration. Patients will be analyzed according to the treatment actually received.

2.3.4 Anti-drug antibody population

The ADA population will consist of all patients in the safety population with at least one non-missing result in the anti-SAR440340 assay following the first dose of IMP. Patients will be analyzed according to the treatment actually received.

2.4 STATISTICAL METHODS

2.4.1 Demographics and baseline characteristics

Continuous data will be summarized using the number of available data, mean, standard deviation (SD), median, minimum and maximum, Q1 and Q3 for each treatment group. Categorical and ordinal data will be summarized using the number and percentage of patients in each treatment group.

Parameters will be summarized on the randomized population analyzed in the treatment group to which they were randomized. Summaries of demographics, baseline disease characteristics and baseline biomarkers will also be provided for the subset of patients with baseline eosinophil count ≥ 250 /mm³. Parameters described in [Section 2.1.1](#) will be summarized by treatment group and overall treatment group using descriptive statistics.

Medical and surgical history will be summarized by treatment group and by primary system organ class (SOC) and preferred term (PT) sorted by internationally agreed order of SOC and by the decreasing frequency of PT within SOC based on the overall incidence across treatment groups. COPD and allergic comorbidity medical history will be summarized separately.

No statistical testing on demographic and baseline characteristic data will be performed.

No specific description of the safety parameters will be provided at baseline. If relevant, the baseline values will be described along with each safety analysis.

2.4.2 Prior or concomitant medications

The prior and concomitant medications will be presented for the mITT population.

Medications will be summarized by treatment group according to the WHO-DD dictionary, considering the first digit of the Anatomic Therapeutic Class (ATC) (anatomic category) and the first 3 digits of the ATC class (therapeutic category). All ATC codes corresponding to a medication will be summarized, and patients will be counted once in each ATC category (anatomic or therapeutic) linked to the medication. Therefore patients may be counted several times for the same medication.

The table for prior medications will be sorted by decreasing frequency of anatomic class followed by decreasing frequency of therapeutic class within anatomic class based on the incidence in the overall group. In case of equal frequency regarding ATCs (anatomic or therapeutic categories), alphabetical order will be used.

Concomitant medications will be summarized for the treatment epoch and treatment emergent period separately. The tables for concomitant medications will be sorted by decreasing frequency of anatomic class followed by decreasing frequency of therapeutic class within anatomic class based on the incidence in the SAR440340 group. In case of equal frequency regarding ATCs (anatomic or therapeutic categories), alphabetical order will be used.

2.4.2.1 Background therapy

Pre-screening background therapy will be summarized by treatment group as LABA + LAMA, ICS + LABA, ICS + LAMA and ICS + LABA + LAMA.

2.4.3 Extent of investigational medicinal product exposure and compliance

The overall extent of IMP exposure and compliance will be assessed and summarized by actual treatment within the safety population ([Section 2.3.2](#)).

2.4.3.1 Extent of investigational medicinal product exposure

The extent of IMP exposure will be assessed by the duration of IMP exposure.

Duration of IMP exposure is defined as last dose date – first dose date + 14 day, regardless of unplanned intermittent discontinuations (see [Section 2.5.3](#) for calculation in case of missing or incomplete data).

Duration of IMP exposure will be summarized descriptively as a quantitative variable (number, mean, standard deviation [SD], median, minimum, and maximum). In addition, duration of treatment exposure will also be summarized categorically by numbers and percentages for each of the following categories and cumulatively according to these categories:

>0 and \leq 8 weeks

>8 and \leq 16 weeks

>16 and \leq 24 weeks

>24 and \leq 32 weeks

>32 and \leq 40 weeks

>40 and \leq 48 weeks

>48 and <52 weeks - 3 days

\geq 52 weeks - 3 days

Additionally, the cumulative duration of treatment exposure will be provided, defined as the sum of the duration of treatment exposure for all patients per treatment arm, and will be expressed in patient years.

2.4.3.2 Compliance

A given administration will be considered non-compliant if the patient did not take the planned dose of treatment as required by the protocol. No imputation will be made for patients with missing or incomplete data.

Percentage of compliance for a patient will be defined as the number of administrations that the patient was compliant divided by the total number of administrations that the patient was planned to take during the treatment epoch defined in [Section 2.1.4](#).

Treatment compliance will be summarized descriptively as quantitative variables (number, mean, SD, median, Q1, Q3, minimum, and maximum). The percentage of patients whose compliance is <80% will be summarized. In addition, numbers and percentages of patients with the wrong dose or an overdose will be summarized.

Cases of overdose (defined as at least twice the intended dose during an interval of less than 8 days) will be listed as such.

2.4.4 Analyses of efficacy endpoints

All efficacy endpoints will be analyzed using the mITT population, unless otherwise specified. In the following and throughout the rest of the SAP, baseline eosinophil strata are defined based on the actual eosinophil count at baseline, which could vary from the stratification grouping used for randomization based on the eosinophil count at screening.

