β-hCG = Human chorionic gonadotropin-beta; BID = twice daily assessments; CAT = COPD Assessment Test; continuous = subsequent visits during the treatment period; COPD = chronic obstructive pulmonary disease; cont. = continuous; DNA = Deoxyribonucleic acid ; EDTA = Ethylenediaminetetraacetic acid ; EOS = End of Study; EOT = End of treatment; EQ-5D= Euro Quality of Life-5 Dimension questionnaire; EXACT = Exacerbations of COPD tool (EXACT); HIV = human immunodeficiency virus; IgE = Immunoglobulin E; IMP = Investigational Medical Product; IVRS = Interactive Voice Response System; IWRS = Interactive Web Response System; LABA = Long-acting β2 adrenergic agonist; LAMA = Long-acting muscarinic antagonist ;PARC = Pulmonary and activation-regulated chemokine; PK = Pharmacokinetic; RNA = Ribonucleic acid; SABA = Short-acting beta-agonists; SAEs = Serious adverse events; SC = subcutaneous; SGRQ = St. George's Respiratory Questionnaire.

a Randomization/baseline Visit is defined as Day 1. The visit schedule should be adhered to within ±3 days for the screening period and randomized IMP treatment period, and ±5 days for the 2 visits during the post IMP treatment period.

b All assessments at Visit 2 (Day 1) are to be conducted pre-IMP dose with the exception of the assessment of local tolerability of SC injections.

c End-of-treatment visit: See Section 4.1 for patients who discontinue treatment.

d Can be performed with a phone call.

e Chest X-ray to be performed unless a <6 month old chest x-ray/chest CT/chest MRI is available. In case chest-X-ray is not feasible due to local regulations, magnetic resonance imaging (MRI) will be performed.

f The COPD Assessment Test (CAT) is to be registered through the patient's electronic diary.

g IMP (SAR440340 or placebo) to be administered every 2 weeks at the site. Last dose will be given 2 weeks prior to planned EOT visit eg, for patients with 52-week treatment period the last dose will be taken at Week 50, or earlier, as directed by the sponsor. Patients should be monitored by site personnel for at least 30 minutes after administration of all IMP injections. Monitoring period may be extended as per country specific requirements.

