6.3 MEASURES TO MINIMIZE BIAS: RANDOMIZATION AND BLINDING

6.3.1 Methods of assigning patients to treatment group

A randomized treatment kit number list will be generated centrally by Sanofi. The investigational product (SAR440340 or matching placebo) will be packaged in accordance with the list. The Sanofi Clinical Supplies team will provide the randomized treatment kit number list to the centralized treatment allocation system (Interactive Voice Response System [IVRS]/Interactive Web Response System [IWRS]). This centralized treatment allocation system will generate the patient randomization list according to which it will allocate the treatments to the patients. Patients who meet the entry criteria will be randomized to receive either SAR440340 or matching

placebo. The Investigator obtains treatment kit number at randomization and subsequent scheduled visits via an IVRS/IWRS that will be available 24 hours a day. Patients will be randomized in a 1:1 ratio to receive SC administrations of either:

- SAR440340 300 mg q2w
- Matching placebo for SAR440340.

Investigational medicinal products will be dispensed at the study visits summarized in SoA ([Section 1.3](#)).

Returned IMP should not be re-dispensed to the participants.

Patients can be rescreened if they do not meet an exclusion criterion. Patients may be rescreened one time if they do not meet the eligibility criteria ([I 02](#)) at the Screening Visit (Visit 1) or Randomization Visit (Visit 2) due to a spirometry equipment malfunction, or because the patient is unable to provide sufficient reproducible efforts. Up to 3 total attempts during the screening visit (V1) are allowed for the reasons mentioned above.

Patients who meet exclusion criteria or who do not meet [I 02](#) as specified above, may be rescreened only once during the open screening period of the study. Rescreening is not permitted if the patient fails to meet inclusion criteria (except for [I 02](#), as described above). For rescreening, see [Section 5.4](#).

Randomization will be stratified by Screening/Visit 1 eosinophil count (see below) and by country.

To ensure scientific validity, alerts will be built into the IVRS/IWRS to control the number of patients enrolled into each stratification group, as follows:

1. Eosinophil <250 /mm³: approximately 50% (170) patients
2. Eosinophil ≥ 250 /mm³: approximately 50% (170) patients

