- Baseline St. George's Respiratory Questionnaire (SGRQ) score
- Baseline Exacerbations of Chronic Obstructive Pulmonary Disease Tool (EXACT) score
- Baseline blood eosinophil count ($< 250 /\text{mm}^3$ and $\geq 250 /\text{mm}^3$)
- Eosinophil count for stratification ($< 250 /\text{mm}^3$ and $\geq 250 /\text{mm}^3$)
- Background therapy containing ICS (Yes/No); if ICS were used, dose of ICS (quantitative variable and qualitative variable: medium, high*)
**Medium: total daily dose of fluticasone = 500 or 460 mcg; high: total daily dose of fluticasone = 1000 or 920 mcg*
- Type of background therapy (Double therapy: LABA + LAMA, ICS + LABA, or ICS + LAMA; Triple therapy: ICS + LABA + LAMA)

Baseline biomarkers

Baseline values of biomarkers, including eosinophils, neutrophils, total IL33, sST2, calcitonin, PARC, eotaxin-3, total IgE, fibrinogen, and FeNO (optional, both pre-BD and post-BD), will be summarized. Eosinophils will be further summarized as

- Baseline blood eosinophil count (quantitative in $< 250 /\text{mm}^3$ and in $\geq 250 /\text{mm}^3$)
- Eosinophil count for stratification (quantitative in $< 250 /\text{mm}^3$ and in $\geq 250 /\text{mm}^3$)
- Baseline blood eosinophil count (quantitative and qualitative < 150 , $150-300$, $\geq 300 /\text{mm}^3$)

Any technical details related to computation, dates, and imputations for missing dates are described in [Section 2.5](#).

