2.4.4.1 Analysis of primary efficacy endpoint(s)

Main statistical model and adjustment of covariates

The primary endpoint is the annualized rate of moderate-to-severe AECOPD.

The primary analysis is a modified intention-to-treat analysis. Off-treatment measurements up to the planned treatment durations for patients who prematurely discontinue treatment will be included for the analysis. The planned treatment duration for a patient is from randomization to the earlier of 52 weeks or 24 weeks after the last patient randomized, ie, patients are treated for a minimum of 24 weeks and a maximum of 52.

The observation duration is equal to the planned treatment duration, except when a patient withdraws early from the study, in which case, the observation duration is from randomization to the last contact of the patient within the planned treatment duration. In the primary analysis, all the exacerbation events that happen in the observation duration will be included, regardless if the patient is on treatment or not.

The primary endpoint of the annualized exacerbation rate will be analyzed using a negative binomial regression model. The model will include the total number of events occurring during the observation period as response variable, and the treatment group, the baseline eosinophil strata and region (pooled countries), number of severe COPD exacerbations experienced in previous year (0 vs. 1+) at baseline, smoking history (current vs. former smoker), post-BD FEV1 percent predicted (<50% vs. ≥50%) at baseline as covariates. Log-transformed observation duration will be the offset variable. Parameters will be estimated using the maximum likelihood method with the Newton-Raphson algorithm. The annualized event rate for the two groups and the relative risk ratio for SAR440340 versus placebo with its 95% confidence interval will be estimated from the model.

Sample SAS code is provided below:

```
proc glimmix data=event;  
class eosblgpn trt01pn cntygrln nscopd csmoker ppredFev1;  
model numevents=trt01pn eosblgpn cntygrln nscopd csmoker ppredFev1  
/offset=logdur dist=negbin link=log solution;  
run;
```

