To assess the consistency of treatment effects across the subgroup levels, subgroup analyses will be performed for the groups listed below. Within each subgroup, descriptive statistics including number of patients, number of moderate to severe AECOPD, treatment exposure time, annualized rate of moderate to severe AECOPD will be provided by treatment group using the same model as for the primary analysis. Risk ratio between treatment and control and the corresponding 95% CI will be provided within each subgroup. Treatment-by-subgroup interaction and its p-value will be derived by a negative binomial regression model. The model will include treatment, baseline eosinophil strata, region, number of severe COPD exacerbations experienced in previous year (0 vs. 1+) at baseline, smoking history (current vs. former smoker), post-BD FEV1 percent predicted (<50% vs. ≥50%) at baseline, subgroup (if different from the aforementioned covariates) and subgroup-by-treatment interaction.

- Blood eosinophil groups (≥ 150 /mm³ versus <150 /mm³, ≥ 250 /mm³ versus <250 /mm³, ≥ 300 /mm³ versus <300 /mm³) defined by actual lab values
- Blood eosinophil groups (≥ 250 /mm³ versus <250 /mm³) from randomization strata.
- Baseline PARC group (<baseline median versus \geq baseline median)
- Baseline Fibrinogen group (<baseline median versus \geq baseline median)
- Age groups (<65 versus ≥ 65 years)
- Sex (Male, Female)
- Region (East Europe: Poland, Russia, Turkey and Ukraine; Latin America: Argentina and Chile; Western countries: USA, Canada, Australia and Germany)
- Race (White, Non-white)
- Background ICS dose level at randomization (none/low, medium, high)
- Baseline CAT score (below median, equal to or above median)

- Baseline post-BD FEV1 percent predicted (<50% vs. ≥50%)
- Baseline weight (<70, ≥70-<90, ≥90 kg)
- BMI (<25, ≥25-<30, ≥30 kg/m²)
- Smoking history (Current, Former)
- Background therapy (triple versus double)

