2.4.4.2 Analyses of secondary efficacy endpoints

2.4.4.2.1 Average change from baseline to Week 16-24 in pre-bronchodilator FEV1

Main statistical model and adjustment of covariates

The key secondary efficacy endpoint, the average change from baseline to Week 16-24 in the pre-bronchodilator FEV1 will be analyzed using a mixed-effect model with repeated measures (MMRM) approach. Model-based average across Weeks 16, 20 and 24 will be compared between the treatment groups. The dependent variable is the change from baseline in pre-bronchodilator FEV1 at each time point. The model will include sex, baseline height, smoking history (current vs. former smoker), baseline FEV1 value, treatment group, visit and treatment-by-visit interaction, baseline FEV1-by-visit interaction, the baseline eosinophil strata, and region (pooled countries) as covariates. An unstructured correlation matrix will be used to model the within-patient correlations. Parameters will be estimated using restricted maximum likelihood method with the Newton-Raphson algorithm. No imputation will be performed on missing FEV1 measurements.

Descriptive statistics including number of patients, mean, standard error, and least squares (LS) means will be provided for each treatment group. Difference in LS means and the corresponding two-sided 95% CI and p-value will be provided for the comparison. Sample SAS code can be found below:

```
proc mixed data=fevldata method=reml;
  class usubjid sex csmoker trt01pn cntygr1 eosbgpln avisitn;
  model chg = sex height csmoker trt01pn trt01pn *avisitn FEV1bl
  FEV1bl* avisitn cntygr1 eosbgpln avisitn
           trt01pn*avisitn /ddfm=kr residual;
  repeated avisitn / subject=usubjid type=un;
  lsmestimate trt01pn*avisitn 'Tx wks 16-24 avg minus pbo wks 16-24 avg' 0 0
1 1 1 0 0 -1 -1 -1/ divisor=3;
  lsmeans trt01pn*avisitn / pdiff cl e;
  ods output LSMeans=LSMeans Diffs=Diffs LSMEstimates=LSMEstimates;
run;
```

If the above model fails to converge, the specification may be changed as follows: 1) use maximum likelihood estimation instead of restricted maximum likelihood method; 2) specify a different covariance structure to reduce the number of unknown parameters to be estimated, the path will be UN→TOEPH→TOEP→AR(1).

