Subgroup analyses of the average change from baseline to Week 16-24 in pre-BD FEV1 will be conducted in the same subgroups as for the primary endpoint based on the primary MMRM model for pre-BD FEV1 described above. Within each subgroup, descriptive statistics including number of patients, mean, SD, and LS means will be provided for each treatment group. Difference in LS means and the corresponding two-sided 95% CI will be provided for the comparison of

SAR440340 and placebo within each subgroup. Treatment-by-subgroup interaction and its p-value will be derived from a MMRM model. The model covariates will include sex, baseline height, smoking history (current vs. former smoker), baseline FEV1 value, treatment group, visit, treatment-by-visit interaction, baseline FEV1-by-visit interaction, the baseline eosinophil strata, region, subgroup (if different from the aforementioned covariates), subgroup-by-treatment interaction, and subgroup-by-treatment-by visit interaction.

2.4.4.2.2 *Change from baseline to Week 24 in post-bronchodilator FEV1*

The analysis method for this endpoint is identical to the analysis of the key secondary efficacy endpoint, the average change from baseline to Week 16-24 in pre-BD FEV1, except that here we only have the value at Week 24, not at Weeks 16 and 20. Similar analysis will be performed for the secondary efficacy population (high EOS group), without the baseline eosinophil strata in the model.

2.4.4.2.3 *Time to first moderate or severe AECOPD*

Time to first moderate or severe AECOPD that occurs from randomization up to week 52 will be analyzed using a Cox regression model with treatment, baseline eosinophil strata and region (pooled countries), number of severe COPD exacerbations experienced in previous year (0 vs. 1+) at baseline, smoking history (current vs. former smoker) and post-BD FEV1 percent predicted (<50% vs. ≥50%) at baseline as covariates. The hazard ratio (HR) between SAR440340 and placebo along with its 95% confidence interval will be estimated by the Cox model. The Kaplan-Meier (K-M) method will be used to estimate the probabilities of first AECOPD at specific time points for each group. P-value from the log-rank test stratified by baseline eosinophil strata and region will be provided.

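### Is it a flaw that the efficacy models adjust for the baseline eosinophil category rather than the Visit 1 stratum used to randomise?

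*SAP*

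**What the plan says.** Protocol section 6.3.1 sets the design: "Randomization will be stratified by Screening/Visit 1 eosinophil count (see below) and by country", with a cut at 250 /mm³. The protocol's efficacy models (synopsis and Table 14) adjust for eosinophil strata described only as baseline, without naming the sample. SAP 2.1.1 defines baseline as the last value before the first dose, which will normally be the Visit 2 sample. SAP 2.4.4 applies that definition to the strata and states that "baseline eosinophil strata are defined based on the actual eosinophil count at baseline, which could vary from the stratification grouping used for randomization".

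The category then enters:
- the primary model (SAP 2.4.4.1), whose terms begin with "the treatment group, the baseline eosinophil strata and region (pooled countries), number of severe COPD exacerbations experienced in previous year";
- the FEV1 MMRM (SAP 2.4.4.2.1), which takes "the baseline eosinophil strata, and region (pooled countries) as covariates";
- the analysis of time to first exacerbation (SAP 2.4.4.2.3), both in the Cox model and in the test: "P-value from the log-rank test stratified by baseline eosinophil strata and region will be provided".

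The randomised grouping is not discarded. SAP 2.1.1 tabulates "Eosinophil count for stratification" beside the baseline category. The subgroup list in SAP 2.4.4.1 includes the 250 /mm³ split "from randomization strata", and pre-bronchodilator FEV1 uses the same list. For time to first exacerbation, the expanded exacerbation endpoint and clinically important deterioration, the SAP plans only the overall analysis and a repeat in patients with a baseline count of at least 250 /mm³.

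**The concern.** Factors used to stratify randomisation normally go into the analysis, because the balance they create lowers the variance of the treatment comparison and a model that ignores it can misstate the standard error. Here the SAP uses a second blood sample and itself concedes that the two groupings can disagree. If many patients crossed 250 /mm³ between Visit 1 and dosing, the models might lose efficiency or have the wrong error rate. The high-eosinophil population, which is defined by baseline count, would also lose the tight arm balance of the randomised stratum. For the time-to-event endpoints, no planned analysis in the randomised high stratum could be set beside it.

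**Working it through.** **1. Validity.** Bias would require a covariate that treatment can affect. Protocol 1.3.1, footnote b, says "All assessments at Visit 2 (Day 1) are to be conducted pre-IMP dose" (the one exception is local injection tolerability). Even if the sample is drawn after allocation, it precedes any drug and the study is double-blind. Both candidate covariates are therefore valid.

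**2. The plan's own figures.** Inputs (Protocol 9.2, SAP 1.3): 170 per arm, dispersion 1.5, two-sided 5% Wald test, and the stated accrual and drop-out. Information per arm = 170 × mean[λt/(1 + 1.5λt)]; power = Φ(|log RR|/SE − 1.96). This gives mean exposure 35.5 weeks (SD 12.8) and power at a 45% reduction of 81.6%, 85.2% and 88.8% for placebo rates 1.0, 1.2 and 1.5, all as stated. No eosinophil term enters, so no stated figure depends on the choice. At rate 1.2 the implied SE is 0.5978/(1.96 + 1.045) = 0.199, where 0.5978 = −log 0.55.

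**3. How many patients could change category.** The documents do not say. For a bivariate normal cut at the median, the share is arccos(ρ)/π. Assuming ρ = 0.7 gives 25.3%, or 0.253 × 340 = 86 patients; assuming ρ = 0.9 gives 14.4%, or 49 patients.

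**4. Effect on the primary analysis, first simulation.** 3,000 trials per scenario, eight scenarios, placebo rate 1.2. Assumed: blocks of 4, ten equally sized countries, ρ = 0.7 or 0.9, and a high-versus-low eosinophil rate ratio of 1.0 or 1.5. The model has treatment, eosinophil term and region.
- Type I error: 5.5–5.9% with the Visit 1 stratum, 5.7–6.1% with the baseline category.
- Power: 85.0–86.2% versus 84.6–86.2%.
- Paired differences: −0.20 to +0.33 points, with Monte Carlo SE 0.13–0.24.

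**5. Effect on the primary analysis, second simulation.** 1,500 trials per scenario, placebo rate 1.2, 10%, 20% or 30% changing category, and the extra risk tied either to the baseline count or to the Visit 1 count. Type I error was 5.1–5.5% (Visit 1 stratum) versus 4.9–5.5% (baseline category); power was 85.0–86.9% versus 85.3–87.6%. Mean rate ratios agreed within 0.001. The 30% scenarios with an eosinophil rate ratio of 1.5 show the pattern:

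| True rate ratio | Count that drives risk | Mean SE, Visit 1 stratum | Mean SE, baseline category | Rejection, Visit 1 | Rejection, baseline |
|---|---|---|---|---|---|
| 1.00 | Baseline | 0.1844 | 0.1834 | 5.07% | 4.87% |
| 1.00 | Visit 1 | 0.1827 | 0.1842 | 5.13% | 5.33% |
| 0.55 | Baseline | 0.2001 | 0.1993 | 85.27% | 85.33% |
| 0.55 | Visit 1 | 0.1991 | 0.2004 | 86.33% | 85.27% |

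The largest gap in SE is 0.1842/0.1827 = 1.008, and its direction reverses with the count assumed to matter. The largest power gap, 86.33 − 85.27 = 1.06 points, is partly noise: those SEs imply Φ(0.5978/0.1991 − 1.96) = 85.1% against Φ(0.5978/0.2004 − 1.96) = 84.7%, about half a point.

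**6. Arm balance in the high-eosinophil population.** Among about 170 patients, the 95th percentile of the arm-size difference d is 6 by randomised stratum and 13–16 by baseline category. Relative information is 1 − (d/n)². With d = 16 the loss is (16/170)² = 0.9%; with d = 13 it is 0.6%.

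**7. What a swap would and would not achieve.** Randomisation is also stratified by country, while the models pool ten countries into three regions (SAP 2.5.6), so the analysis would still not follow the design's strata. The high-eosinophil analyses drop the eosinophil term because it is constant in that population; a Visit 1 covariate would not be constant there. The SAP's single eosinophil definition would become two, and the arm balance in step 6 would not change.

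**The case for a change.** The strongest argument is textual. The only eosinophil strata the protocol sets up are the Visit 1 groups (sections 6.3.1 and 9.2), and for subgroups it speaks of levels rather than strata. A reader could take the protocol's covariate to be the randomised stratum, and SAP 1.5 does not list the choice among its modifications. The ambiguity is real. The adjective is still baseline, though, and both documents define baseline as the last value before dosing (Protocol 9.4.2, for safety data; SAP 2.1.1 in general). The SAP settles the reading and contradicts nothing.

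It is also true that no main or sensitivity model uses the randomised stratum in place of the baseline category, that the two groupings are tabulated separately rather than crossed, and that time to first exacerbation has no split by randomised stratum. However, that endpoint has no subgroup list at all, and the exacerbation rate, which counts the same moderate-to-severe events, is already split by randomised stratum. With no multiplicity control and nominal p-values throughout (SAP 2.4.4.4), a further split would be descriptive. A cross-tabulation would be helpful to readers, but its absence is not an error.

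The imputation code in SAP Appendix J uses a variable named STRATUM1 of unclear origin. The appendix says the code is explanatory and that the main text determines the covariates.

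**Conclusion.** The concern does not hold. The SAP pre-specifies a pre-dose covariate, discloses that it can differ from the randomisation grouping, and stays within the protocol's wording. No bias arises. Across the scenarios examined, the choice moves type I error or power by at most about 1.1 points, part of which is simulation noise, and the mean rate ratio by at most 0.001. Neither covariate is reliably the more efficient. The looser arm balance in the high-eosinophil population costs under 1% of information at the 95th percentile.

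These sizes rest on assumptions that are not in the documents: 10–30% of patients changing category, an eosinophil rate ratio of 1.0–1.5, and, for arm balance, blocks of 4 and equal country shares. Both simulations left out the remaining SAP covariates, and the first had a mean exposure of 35.0 weeks against the stated 35.5. The simulations cover the negative binomial model only. For the MMRM, Cox and log-rank analyses the conclusion rests on the validity argument in step 1, which does not depend on the model. Choosing between the two covariates is a matter of preference.
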